**OBJECTIVES**

Determine whether Mesh Suture achieves an acceptable safety and efficacy profile with the appropriate performance for internal load bearing closures, and with acceptable risks and benefits.

**STUDY TIMELINES**

It will take approximately 12 months to accrue 80 patients into the study. The patients will be followed 1 year after the implantation of the mesh suture. It will take approximately 3 months to collect the data after the final patient has had their one-year final examination.

---

## **STUDY ENDPOINTS**

30 days and 12 months

## **PRIMARY OUTCOMES**

### **1. Surgical site occurrence (SSO) within 30 days**

- Superficial infection
- Deep infection
- Dehiscence
- Hematoma
- Necrosis
- Non-healing wound
- Seroma

### **2. Delayed infection or sinus within 1-12 months**

- Office removal of suture or knot
- Return to the operating room (OR) for draining wound
- Knot removal for palpability (added April 20, 2019)

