## **SAFETY AND EFFECTIVENESS**

This safety and effectiveness study is intended to demonstrate that overall patient outcomes are no worse than or adversely different from the current surgical standard of care. In addition to overall patient outcomes, the study will also examine adverse outcomes related to the use of the suture.

An overarching issue is that the suture used in the procedure reflects only a small part of the total treatment of the patient – including what adverse occurrences are responsible for surgical morbidity and mortality. Robust evaluation of suture closures is best assessed in the setting of an animal study where the surgical wound can be opened and tested at the end of the follow-up period. This then allows the investigator to readily inspect the suture line and assess the abdominal suture closure for safety and effectiveness endpoints including suture pull-through. This is not possible in the treatment of humans. Therefore, safety is best noted by the achievement of standard wound healing rates and the absence of delayed infections in comparison to historical controls. Efficacy is best noted by the achievement of standard functional outcomes in comparison to historical controls.

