**POTENTIAL RISKS TO PARTICIPANTS**

The Mesh Suture will be manufactured (fabrication, sterilization and packaging) using GMP standards by one of the largest suture companies in the world, Surgical Specialties. The risk of contamination or inadequate preparation is very low considering the experience of the manufacturer. This will minimize the risk of an issue with the suture itself (sterility, composition, tensile characteristics, etc.) to the patient.

The overwhelming majority of risks to the patient is inherent to surgery and the surgical process, and is not relatable or attributable to the suture used for closure. The risks of surgery as delineated in this submission far outweigh any ADDED risks of using Mesh Suture for closure as opposed to standard suture. There are risks of the use of a permanent suture in terms of delayed infection.

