**OBSERVATION AND RECORDING OF RESULTS**

Will be performed by the PI and his designees based on the routing performance of clinical practice. Superficial infection will be defined as the use of oral antibiotics for erythema that is more consistent with a bacterial process than with other explanations including pressure induced erythema, allergic reactions of the skin, or irritation from skin sutures. A deep infection is defined as purulent drainage from the wound requiring an opening of the skin by the surgeon, a return to the operating room for drainage or wounds, and/or cultures from internal structures consistent with an infection. Hematoma is defined as a collection of blood as the primary cause of a lack of appropriate wound healing, and a hematoma with secondary infection of the clot is also defined as a hematoma. A seroma is defined as clear fluid found underneath an intact incision or draining through a wound as the primary cause of a lack of appropriate wound healing. A delayed sinus is defined as a area of a previously healed incision that leads to the Duramesh knot or filament that does not resolve with antibiotics, or requires an opening of the wound and Duramesh removal for resolution.

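### Primary outcome 2 is named delayed infection or sinus, but its listed items are procedures that include non-infectious suture or knot removals, so a count over the list is not a delayed-infection rate

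*Protocol*

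**What the plan says.** Under Primary Outcomes, the second outcome is named as delayed infection or sinus in months 1 to 12. Three items follow: "Office removal of suture or knot", a return to the operating room (OR) for a draining wound, and "Knot removal for palpability (added April 20, 2019". The dated item stands in the current outcome list, not in a change log. The protocol does not say whether the three items are the whole definition, examples, or additions to the named event. The synopsis table repeats the outcome name as a primary safety endpoint, without the items.

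Observation and Recording of Results gives clinical definitions:

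- Superficial infection: "Superficial infection will be defined as the use of oral antibiotics for erythema that is more consistent with a bacterial process".
- Deep infection: "A deep infection is defined as purulent drainage from the wound requiring an opening of the skin by the surgeon", or a return to the OR for drainage, and/or positive cultures from internal structures.
- Delayed sinus: a tract in a healed incision leading to the knot or filament "that does not resolve with antibiotics, or requires an opening of the wound and Duramesh removal for resolution".

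There is no separate entry for delayed infection.

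The outcome carries weight elsewhere. Safety and Effectiveness rests safety partly on "the absence of delayed infections in comparison to historical controls". Potential Risks to Participants states: "There are risks of the use of a permanent suture in terms of delayed infection". Closure of the Study makes a lack of early and late infections part of the early-closure judgement. Final Report requires an evaluation of all primary endpoints.

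**The concern.** The name describes a clinical event and the list describes what was done about something. These are different quantities. A knot removed because the patient can feel it is a real device problem, but it is not an infection. An office removal with no reason attached may or may not follow one.

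The trial has a single arm and judges safety against historical controls. If the primary outcome mixes infections with removals for other reasons, its rate cannot be set beside a historical rate of delayed infection, even informally. This is one of only two primary safety endpoints, and it addresses the one hazard that the protocol itself attaches to a permanent suture.

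**Working it through.** The protocol gives no rate, margin or power for this outcome, so there is no stated figure to reproduce. The check is a comparison of texts, followed by a statement of scale.

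**Step 1: each listed item against the outcome name.**

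- Office removal of suture or knot: a procedure, with no reason required. It can be counted without infection or sinus.
- Return to the OR for a draining wound: a procedure tied to drainage, not to a confirmed infection.
- Knot removal for palpability: a procedure whose stated reason is non-infectious.

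All three items are procedures. One is outside the outcome name by its own wording, and one does not require the named event.

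**Step 2: each clinical definition against the list, for onset in months 1 to 12, if the list were exhaustive.**

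- Superficial infection, defined by oral antibiotics for erythema: no item.
- Deep infection met by opening the skin or by culture, without suture removal or OR return: no item.
- Deep infection met by OR return for drainage: covered by the second item.
- Sinus needing wound opening and Duramesh removal: covered by the removal item, or by the OR item if drained there.
- Sinus that does not resolve with antibiotics and is left in place: no item.
- Sinus that resolves with antibiotics: not a delayed sinus under the protocol's definition, so no gap arises.

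The sinus gap is therefore narrow. The infection gap is wider, but it depends on carrying the general infection definitions past day 30, which the protocol neither does nor rules out.

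**Step 3: scale.** The protocol gives N = 80; assume that all 80 are evaluable. One patient is 1/80 = 1.25 percentage points. Let m be the non-infectious removals counted and k the infection or sinus events with no item. Then

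listed rate − infection-or-sinus rate = (m − k)/80.

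The protocol gives neither m nor k. With assumed values of 0 to 2 for each:

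- List not exhaustive (k = 0): 0 to 2/80, that is 0 to +2.5 points.
- List exhaustive: −2/80 to +2/80, that is −2.5 to +2.5 points.

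The symmetry of the second range comes from the assumed counts, not from the documents. For sampling error at this size, exact (Clopper-Pearson) 95% intervals are 1/80 = 1.25% (0.03 to 6.8) and 3/80 = 3.75% (0.8 to 10.6). They overlap widely.

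**Step 4: could the protocol's own series serve as a reference?** They report such events separately:

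- Office knot removal: 1/107 = 0.9% (0.02 to 5.1), section 2.1.3.
- OR return for a deep infected knot: none, section 2.1.4. The sentence opens with the 49 patients with contaminated fields, so the denominator may be 107 (upper limit 3.4%) or 49 (upper limit about 7.3%).
- Delayed suture sinus: 0/48 (upper limit 7.4%), section 2.2.3.

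These are not like-for-like comparators. They are abdominal closures with strips cut from mesh, and mean follow-up in the 107-patient series was 234 days, against 12 months here.

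**The case against.** The best defence is that the heading is the definition. The synopsis repeats the name without the list, other sections speak of delayed or late infections as such, and the final follow-up asks for possible delayed infection to be assessed. On that reading an infection counts whatever was done about it, and the items are additions. Bullets have no fixed meaning in this protocol: under the secondary outcomes they are rating scales or response categories. Only the first primary outcome, "Surgical site occurrence (SSO) within 30 days", uses the same layout for component events. This defence stands against the omission half. A reader might infer that infections managed without a procedure are left out of the primary outcome; the documents do not establish that. It does not rescue the palpability item, which does not fit the name on either reading.

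Second, the protocol does not say that the items are pooled. Palpability has its own line and could be reported alone; a pooling rule, or a field for the reason for removal, may sit in a statistical plan or case report form (CRF) that is not at hand. That stands as a limit: the point concerns a count over the list as written.

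Third, the data monitoring committee classifies complications by relatedness to the suture and settles doubts over adverse-event category, and a clinical events committee also reviews outcomes. But relatedness is a different question: a palpable knot is related to the suture without being an infection.

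Fourth, confining the late outcome to suture-related events would be a defensible choice, and counting all erythema treated with antibiotics up to 12 months would broaden it. That is fair. It is a reason for the protocol to state its choice.

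A reader might also infer that the 2019 addition answered events already seen, or that it favours the device. The protocol gives only a date, and adding an event type can only raise the count.

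**Conclusion.** The mismatch between name and list is present in the current text. A count over the listed items includes non-infectious removals and cannot be read as a delayed-infection rate. This rests on wording alone and needs no assumption about event counts.

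The possible omission of infections, or of an unresolved sinus left in place, is an ambiguity. It arises only if the list is exhaustive and, for infections, only if the general definitions apply after day 30.

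The numerical effect is 1.25 points per misclassified patient. The total and the net direction are unknown, so no bias is shown. Nor are safety data lost: cases without an item should still be recorded as adverse events, and every return to the OR in months 1 to 12 is a secondary outcome. No sample-size calculation depends on this list, and the moratorium rules use surgical site occurrence, dehiscence and death. The point should be corrected because it affects the meaning of a primary safety outcome, but it does not undermine the trial.

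**What to change.** Reconcile the primary outcome list, the synopsis table and Observation and Recording of Results:

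1. State that primary outcome 2 counts delayed infection or sinus in months 1 to 12 as the event, however it is managed.
2. State which of the superficial and deep infection definitions apply after day 30, since delayed infection has no definition of its own. Say whether the present sinus definition, which leaves out a sinus that resolves with antibiotics, is kept.
3. Report suture or knot removal for palpability or any other non-infectious reason as a separate device-safety outcome, so that nothing now listed is dropped.
4. Record the reason for each removal on the CRF, if it is not already there.

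The cost is protocol and CRF wording and at most one extra field; no visits are added. The downside is that the infection rate may be slightly less favourable, if infections managed without a procedure would otherwise have gone uncounted, and removals must be read from a second line.

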## **SECONDARY OUTCOMES**

### **1. Operating room handling of suture**

- Surgeon satisfaction with suture for repair of tissues (min 1, max 5)
- Intraoperative suture breaking or fraying (min 1, max 5)
- Quality of knot (min 1, max 5)
- Needle size and shape appropriate (min 1, max 5)

### **2. Rehospitalization for any wound issue within 30 days**

### **3. Return to the OR for any reason within 1-12 months**

### **4. General rating of the suture by surgeon**

- Excellent
- Good
- Fair
- Poor

## **INCLUSION CRITERIA**

Consecutive patients undergoing planned surgery at the Wigmore Clinic and Arabkir Joint Medical Center in Yerevan, Armenia, and requiring deep soft tissue approximation and/or ligation:

1. Age: more than 1 year
2. Gender: male or female
3. Indications for use: tendon lengthening, ligamentoplasty, tendon repair, repair of joint capsules, other deep tissue approximations

## **EXCLUSION CRITERIA**

1. No planned need for closure of deep soft tissues
2. Pregnancy
3. Age less than 1 year
4. Repair of skin or other tissues with epithelium

Indications for Use	The Mesh Suture is indicated for use in soft tissue approximation and/or ligation. Not to be used for the skin.
Patient Population	Subjects will be recruited from a population of patients treated for orthopedic conditions by [name]
Study Size and Center	N=80 patients at Wigmore Clinic Arabkir Joint Medical Center in Yerevan, Armenia
Clinical Study Design	Safety and efficacy trial of a medical device (surgical suture). Prospective, Non-blinded and non-randomized, Multi-center, Single-surgeon
Primary Safety Endpoints	Surgical site occurrence (SSO) with 30 postoperative days Delayed infection or sinus within 1-12 months
Secondary Effectiveness Endpoints	Operating room handling Rehospitalization for any wound issue within 30 days Return to the OR for any reason within 1-12 months General rating of the suture by surgeon
Study Flow	
SCREENING
 
 
1. Preoperative assessment by the surgeon to confirm that the patient meets the study entry criteria.
 
2. Informed consent obtained from patient by study staff.
 
 
SURGERY
 
 
1. Perform surgery and close deep tissues with Mesh Suture
 
2. Record intraoperative information on CRF.
 
 
PATIENTS EXCLUDED FROM FURTHER FOLLOW-UP
 
Based on the tissues, patient's condition, and all other intraoperative factors, [name] may decide not to use a mesh suture. These patients will not undergo any further follow-up nor be included in the safety and effectiveness analyses.
 
INITIAL FOLLOW-UP
 
Patient follow-up will be per [name] established protocols. All patients will be seen at least or contacted by study staff by 30 days to assess healing of the incision and assess for possible SSO.
 
FINAL FOLLOW-UP
 
Late patient follow-up will be per [name] established protocols. All patients will be seen at least or contacted by study staff by the end of the study period (12 months after the surgery) to assess healing of the incision, functional outcome of surgery, and assess for possible delayed infection.

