### **CLOSURE OF THE STUDY**

For this first-in-human use of mesh suture, 80 cases will be performed in this safety and effectiveness study. The hypothesis is that the mesh suture will be equivalent in performance to standard suture. The study will be closed upon accrual of 80 patients, final follow-up of these patients. An early moratorium of the study will occur with a 15% rate of SSO, or 3 early and unexpected dehiscences of deep tissue closure attributable to the suture as judged by the data monitoring committee. Early closure of the study will occur based on the judgement of the PI, the sponsor, and an early demonstration of equivalence to the results of standard suture as judged by a lack of early and late infections and appropriate postoperative surgical results demonstrating appropriate tissue approximation for internal load-bearing closures.

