**NUMBER OF LOCAL PARTICIPANTS**

It is anticipated that up to 100 patients will need to be consented preoperatively to have 80 patients who will have the potential to have an internal mesh suture closure.

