#### **DRUGS OR DEVICES**

Three different sizes of Mesh Suture, namely 2-0, 0 and Number 2, will be under the control of the study coordinator, and will be disbursed in the operating room at the time of the procedure. The study coordinator will fill out the necessary patient data form at that time. For traceability, lot number and expiration date for finished and packaged suture will be recorded. The sutures will be locked in a cabinet in the operating room with keys controlled by Drs. [name] and [name]. They are labelled "For investigational use only".

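### The rule dropping patients in whom mesh suture is not used does not separate sutures never attempted from sutures attempted and abandoned, so it may remove some intraoperative failures and exposed patients

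*Protocol*

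**What the plan says.** The rule is in the Study Flow table, printed under the exclusion criteria. The grounds for the decision are open: "Based on the tissues, patient's condition, and all other intraoperative factors". On those grounds the operating surgeon "may decide not to use a mesh suture". The consequence is fixed: "These patients will not undergo any further follow-up nor be included in the safety and effectiveness analyses". The table lists this step after the surgery steps, which include "Record intraoperative information on CRF".

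Three other places bear on it.

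- **Secondary outcome 1 (operating room handling)** covers surgeon satisfaction, knot quality, needle suitability and "Intraoperative suture breaking or fraying (min 1, max 5"). These are ratings from 1 to 5, and the protocol defines no failure level on them.
- **Number of Local Participants** sets the consent allowance: "It is anticipated that up to 100 patients will need to be consented preoperatively to have 80 patients who will have the potential". The potential meant is closure with mesh suture. The protocol gives no reasons for the difference.
- **Closure of the Study** describes first-in-human use and says that "80 cases will be performed in this safety and effectiveness study".

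The design is single-arm and unblinded, with one surgeon.

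**The concern.** Leaving out patients who never met the device is normal in a device study. The difficulty is that the rule turns on a decision not to use the suture and never says what counts as use. A surgeon who opens a pack, passes the needle, sees the suture fray and finishes with a conventional suture could reasonably file the case either way. One of those readings removes it from everything.

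Two things are at stake. First, a suture bad enough to be replaced is the most informative observation for the handling outcomes. If such cases can leave, the scores become partly conditional on the suture having worked well enough to be kept. The person who decides on non-use also rates the suture. Second, a patient whose tissue was crossed by the needle, or who retains some filament, would lose the 30-day and 12-month contacts and drop out of the safety denominator. A later analysis plan cannot repair this, because the protocol stops the data collection itself.

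**Working it through.** **Step 1. Which patients the rule reaches.** Take each situation in turn against the text.

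| Situation in surgery | Handling scores | 30-day and 12-month follow-up | Clear from the text? |
|---|---|---|---|
| Mesh suture never opened | Out | Out | Yes |
| Mesh suture breaks or frays, closure still completed with mesh suture | In | In | Yes |
| Pack opened, suture rejected before passage | Not stated | Not stated | No |
| Suture passed through tissue, then abandoned and replaced | Not stated | Not stated | No |

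The first two rows are sound. The gap is confined to the last two.

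**Step 2. Whether another section closes the gap.** Under Drugs or Devices, suture is dispensed in the operating room and "The study coordinator will fill out the necessary patient data form at that time". Traceability requires lot, reference and expiry details for each case. Adverse events and complications are to be documented and reviewed, and the final report includes a qualitative account of problems in use. These make it more likely that an attempt leaves a trace. None of them returns the patient to follow-up or analysis, and none asks for the number of, or reasons for, non-use.

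**Step 3. How much it could matter.** The protocol gives no abandonment count, so there is no figure to reproduce. Inputs: 80 planned cases (Closure of the Study) and up to 100 consented (Number of Local Participants), hence up to 100 − 80 = 20 consented patients, or 20/100 = 20%, outside the 80. Let k be the number of attempted and abandoned cases that are dropped. **k is an assumption**; the range 0 to 20 is only an outer bound, taken from the consent allowance.

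Share of all attempts missing from the handling results = k / (80 + k).

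- k = 0: 0/80 = 0%
- k = 2: 2/82 = 2.4%
- k = 5: 5/85 = 5.9%
- k = 10: 10/90 = 11.1%
- k = 20: 20/100 = 20.0%

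The result is similar if some problems are also seen among the 80 retained patients. Assume 4 of 80 (5.0%) had one. Restoring the dropped cases gives (4 + k)/(80 + k): 6/82 = 7.3%, 9/85 = 10.6% and 14/90 = 15.6% for k = 2, 5 and 10.

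These are shares of patients. They are not an endpoint of the protocol, which defines ratings and no failure rate.

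**Step 4. Direction.** For handling, the dropped cases are by construction the poor ones, so the shift favours the device whenever k is above zero. For safety, the loss of exposed patients from the denominator is certain on the broad reading, but the complication rate moves in the device's favour only if those patients fare worse than the rest. The protocol gives no information on that.

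**The case against.** The strongest reply is that a decision not to use a suture most naturally means that none was used. On that reading, a suture that was passed or partly placed has been used, and the patient stays in. The grounds actually named are the tissues and the patient's condition; handling is not mentioned. This stands as the more natural reading, and it rules out saying that the protocol excludes failed attempts. It does not settle the matter, because the catch-all wording on intraoperative factors has no limit and the surgeon applying it must choose.

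A reader might go further and infer that the study omits the device's intraoperative failures altogether, or would report none among 80. The protocol does not support either. Breaking, fraying, knot and needle problems are rated outcomes, and such problems in patients still closed with mesh suture are kept.

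A reader might also take the up to 20 extra consented patients as abandoned sutures. Nothing links them. The sentence speaks of obtaining 80 patients with the potential for mesh suture closure, so the others may never have come near the device.

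It is also fair to say that the clearest effect falls on a secondary, surgeon-rated outcome. No effect on the primary safety outcomes can be quantified.

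**Conclusion.** The point holds as an ambiguity with a one-sided risk. The rule does not distinguish *never attempted* from *attempted and abandoned*. Read broadly, it drops poor handling cases and exposed patients from a first-in-human study, at the discretion of one unblinded surgeon. Bias has not been shown: the number of such patients is unknown, and if it is zero nothing changes. Under assumed counts of 2 to 10, between 2.4% and 11.1% of attempts would be missing from the handling results. This rests on the 80 being completed mesh suture closures and on the assumed counts, which have no source in the protocol. It is worth correcting because the correction is cheap and follow-up that was never done cannot be recovered.

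**What to change.** Amend the Study Flow table along these lines:

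- The exclusion applies only when no mesh suture was opened for use on the patient.
- Any patient for whom a pack was opened or a needle passed is scored on the handling outcomes. Abandonment is reported as a separate count and is not forced onto the 1-to-5 scales.
- Any patient in whom mesh suture was passed through tissue stays in the safety analysis and receives the existing 30-day and 12-month contacts.
- The reason for non-use or abandonment is recorded on the intraoperative CRF. The final report gives the number of, and reasons for, each among all consented patients.

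Using pack opening as the trigger for handling matters: a suture rejected for its needle, or frayed before passage, would be missed if only passage through tissue counted.

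The cost is a short wording change, one CRF field and a few more follow-up contacts. The handling results may look slightly less favourable.

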## **PATIENT SELECTION**

Will be at the discretion of the PI, with patients matching inclusion criteria and not have any exclusion criteria. The patient should be able to have postoperative follow-up visits and have the appropriate guardians to provide consent if under the age of 18.

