## **MISSING DATA**

It is the responsibility of the PI to accurately and completely fill out the CRF. Missing data will be analyzed by the data monitoring committee and completed with assistance of the PI. Follow-up either in person at the Wigmore Clinic or by telephone is the responsibility of the PI.

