## **FINAL REPORT**

A final report of data will be provided by the PI to the sponsor. This will include an evaluation of all primary and secondary endpoints. Efforts will be made to obtain long term follow up either by office visits at the Wigmore Clinic, and/or telephonic interviews of subjects. Duramesh will be analyzed in terms of the size used, the location placed (tendon, joint capsule), running or interrupted closure, surgeon satisfaction, and a qualitative report of issues of use of the suture. The appropriate statistical tests including t-tests for the comparison of groups will be employed for data analysis.

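### The 30-day SSO check may be done by telephone, although superficial infection, seroma and hematoma are defined by judgements that need someone to look at the wound

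*Protocol*

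**What the plan says.** The Study Flow table (Protocol, under Exclusion Criteria) first says that follow-up runs according to the surgeon's established protocols, which are not described. It then sets a minimum for the 30-day SSO check: "All patients will be seen at least or contacted by study staff by 30 days to assess healing of the incision". This same contact is the one that looks for SSO. The 12-month check has the same form: "All patients will be seen at least or contacted by study staff by the end of the study period (12 months after the surgery").

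The table says only that patients may be contacted. The telephone is named in Missing Data: "Follow-up either in person at the Wigmore Clinic or by telephone is the responsibility of the PI". Final Report adds: "Efforts will be made to obtain long term follow up either by office visits at the Wigmore Clinic, and/or telephonic interviews of subjects".

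Observation and Recording of Results gives the definitions. For seroma it begins: "A seroma is defined as clear fluid found underneath an intact incision". It then adds drainage through a wound, and the fluid must be the main reason for poor healing. Hematoma is a blood collection judged to be that main reason. Superficial infection is oral antibiotic treatment for redness judged more likely bacterial than due to pressure, allergy or skin-suture irritation.

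Two other places assume attendance. Study Timelines counts the data-collection period from the time "after the final patient has had their one-year final examination", and Patient Selection says "The patient should be able to have postoperative follow-up visits".

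**The concern.** A site can meet the stated 30-day requirement for every patient without anyone looking at a wound at that check. Three of the seven listed SSO components carry definitions that turn on the cause of redness or on why a wound is healing poorly. A caller has only the patient's account or, for the children the trial admits, possibly a guardian's.

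The trial has one arm. Safety and Effectiveness judges safety against historical controls, so no concurrent group shares any under-detection. The same SSO count drives the 15% moratorium in Provisions to Monitor the Data and in Closure of the Study. The latter also lets a lack of early and late infections support early closure for equivalence. Missed events would push all of these in the device's favour.

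**Working it through.** The protocol gives no detection rate, telephone share or expected SSO rate, so there is no figure of its own to reproduce. The check is a reading of the text, followed by an illustration.

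**1. What a telephone contact can establish**

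- *Superficial infection:* antibiotic use can be reported or found in records. The judgement on the cause of the redness needs an examiner at some point.
- *Seroma and hematoma:* these need fluid or blood to be identified and judged the main cause of poor healing. Drainage may be reported; fluid under an intact incision is hard to establish by call.
- *Deep infection:* largely marked by wound opening, return to the operating room or culture, so interview or records can find it.
- *Dehiscence, necrosis, non-healing wound:* listed as SSO components but not defined in Observation and Recording of Results, so no argument is built on them.
- *12-month outcome:* the listed items are office removal of suture or knot, return to the operating room for a draining wound, and knot removal for palpability. All are procedures. The sinus definition requires failed antibiotics, or wound opening with removal, so such a patient has already been treated.

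The exposure therefore lies mainly in the 30-day outcome.

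**2. Illustration of the rate**

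N = 80 is from the protocol; everything else is assumed. Let p be the true SSO rate, f the share followed by telephone only, and s the share of their events that telephone contact finds. Examined patients are taken as fully detected.

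Observed rate = p × [1 − f × (1 − s)]

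With p = 10% (8 of 80) and s = 0.5:

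- f = 0.2: 10% × (1 − 0.10) = 9.0%, or 7.2 of 80
- f = 0.4: 10% × (1 − 0.20) = 8.0%, or 6.4 of 80
- f = 0.8: 10% × (1 − 0.40) = 6.0%, or 4.8 of 80

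**3. Illustration of the moratorium**

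Applying the 15% threshold to the full sample (an assumption) gives 0.15 × 80 = 12 events. At a true SSO rate of 20%, the binomial probability of at least 12 observed events in 80 is 0.899 with full detection. With half the patients on telephone only (f = 0.5):

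- s = 0.9: observed rate 19.0%, probability 0.855
- s = 0.7: observed rate 17.0%, probability 0.727
- s = 0.5: observed rate 15.0%, probability 0.548

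**The case against.** The strongest reply is that the seen-or-contacted rule is a floor added to routine surgical follow-up. Observation is by the investigator and designees in ordinary practice, and Data from the Medical Record gives access to operative reports, photographs, laboratory and culture results. Many events may be caught before any call, and nothing says that telephone-only follow-up will be common. The telephone sentence also stands under Missing Data, so it can be read as a fallback. No passage says that a call is coded as no event; coding may sit in a case report form (CRF) or SAP that is not shown.

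Much of this stands, and it is why the size cannot be stated. It does not remove the point: the established protocols are not described, the telephone sentence contains no fallback limit, and no passage requires an examination for the 30-day check.

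A reader might infer more than the text supports:

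- *That both primary outcomes are equally affected.* The 12-month items are procedures, so they are not.
- *That deep dehiscence under healed skin would be missed by telephone and so escape the moratorium.* Dehiscence is not defined, and a wound examination would not reliably show such a separation either.
- *That the telephone allowance contradicts Study Timelines and Patient Selection.* One is a timeline sentence and the other a selection condition. Neither sets a visit, so there is tension but no contradiction.

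**Conclusion.** The point holds for the 30-day SSO outcome. The protocol accepts a contact in place of a visit, while defining superficial infection, seroma and hematoma by judgements that need the wound to be seen. A fully compliant follow-up can therefore under-count SSO.

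The likely direction is a lower observed rate for the device and a weaker moratorium. This assumes that telephone contact yields few false positives and that the historical controls were assessed at least as closely; the documents do not describe how those controls were assessed. The size is unknown: the 9.0% to 6.0% range and the moratorium probabilities show how the bias would act under assumed inputs and are not estimates for this trial. The 12-month outcome is much less exposed. The change is worth making because wounds not examined in time cannot be examined later.

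**What to change.** - In the Study Flow table and Missing Data, make an in-person wound assessment, at either site, the default for the 30-day SSO check.
- Reconcile the 12-month seen-or-contacted wording with the final examination named in Study Timelines.
- Allow telephone only as a fallback when attendance fails, supplemented by the records available under Data from the Medical Record.
- Record the mode of contact on the CRF.
- Do not code examination-dependent SSO components as event-free on a telephone contact alone unless an earlier examination or record supports it.
- Report SSO by mode of contact.

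The cost is wording in two places, one CRF field and a coding rule. Some patients must attend a visit they might otherwise have skipped, and a few will be non-evaluable for some components. The change concerns how outcomes are ascertained and leaves treatment as it is.
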